2.3 Sample and Consent

Study participants were recruited from all middle school students (grades 6-8) in Blatchley Middle School in Sitka, Hoonah City School in Hoonah, and Dzantik'i Heeni Middle School in Juneau. The program enrolled 11 participants in Sitka, 20 in Hoonah, and 19 in Juneau for a total of 50 participants across communities. Research participation was not required to participate in the education program, and students opted into the survey and interview research components through a tiered informed consent process. Written consent was obtained from parents after information on research activities was shared, and verbal consent was obtained from participants before data collection activities. Of the 50 study participants, all consented to participate in the surveys and all but one consented to participate in the interviews. Participants in either or both research components were offered a \$10 cash card incentive for each lesson attended, with a total possible incentive of \$100 for attending all ten lessons. Incentives were used to encourage program participation and regular attendance.

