2.4 Survey Design

A five-point (1-5) Likert scale survey was administered to participants at the beginning and end of the program, as well as one year after program completion. The instrument used in

these three instances of data collection included 16 questions relevant to the three types of TPB beliefs—behavioral beliefs (attitudes toward the behavior), normative beliefs (perceived attitudes of peers and respected figures toward the behavior), and control beliefs (perceived ability to perform the behavior)—and was divided into two sections. In the first section, on shellfish harvesting, questions asked about participants' perceptions of and experience with shellfish harvesting, perceptions of peers' views about shellfish harvesting, and sense of agency and behavioral intentions related to engaging in shellfish harvesting. For example, related to normative beliefs: "Most of the people who are important to me would approve of me participating in subsistence clam harvesting" (disagree – agree Likert scale). In the second section, on checking toxin levels using the SEATOR website, questions asked about participants' perceptions of this risk reduction behavior, perceptions of peers' views about checking toxin levels, and sense of agency and behavioral intentions related to checking toxin levels. For example, related to control beliefs: "I am confident that I can check the SEATOR website before clam harvesting" (disagree – agree Likert scale). In both sections, the last question asked about behavioral changes related to program learning and thus was relevant in only the post-program survey. Full survey response data is presented in appendix 2.

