2.5 Survey Data Analysis

2.5.1. Accounting for Missing Data

Missing data at the person-visit level were imputed for age (n missing = 6) and each of the questions (n missing = 9-20, depending on question), treating each person-visit as a separate observation. The predictor variables in the imputed model included all question responses and all regression model predictors: age, gender identity, Alaska Native identity, and site. We used listwise deletion, excluding cases from analysis if data was missing, for gender (n missing = 10), Alaska Native identity (n missing = 6), and pre-post-program differences (n missing = 9-15, depending on question). No site data was missing. We generated 80 imputed

datasets via multiple imputation by chained equations (Azur et al., 2011). Across our models, the largest average relative increase in variance (RVI) due to nonresponse was 0.44 and the largest fraction of missing information (FMI) was 0.55, suggesting that our analysis based on 80 imputed datasets was reasonable. Statistical analyses were conducted using STATA 18.0 M/P (StataCorp, 2023).

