2.5.2. Pre-Post-Program Changes in Theory of Planned Behavior Beliefs and Behavioral Intentions

To evaluate pre-post-program changes in beliefs and behavioral intentions related to shellfish harvesting, consumption, and risk reduction, we tested the association between pre- and post-program responses (i.e., the intervention effect). We included covariates for site (Sitka, Hoonah, and Juneau), age, Alaska Native identity (Alaska Native, non-Native), and gender identity (girls, boys, and nonbinary). To consider within person pre-post-program changes in TPB Beliefs and behavioral intentions, we used generalized estimating equation linear regression (GEE) to cluster pre-post measures (Liang & Zeger, 1986). We also evaluated differences in pre-post-program changes in TPB beliefs and behavioral intentions among the three participating communities and Alaska Native and gender identities using interacted models. Results of interacted models are presented in appendix 3.

We present individual participants' responses to the one year post-program survey as the number of participants in this follow-up survey was small. When we closed the study on July 31, 2024, only 7 participants had completed the program at least one year prior and were available for one year post-program recontact, having completed the program in either fall 2022 or spring 2023 semesters. These participants were all from Sitka. Of these 7 participants, 4 completed the follow-up survey. One year post-program survey responses are presented in appendix 4.

2.5.3. Relationships Between Changes in Theory of Planned Behavior Beliefs and Changes in Behavioral Intentions

To characterize TPB constructs most influential in shifting planned behaviors, we again used GEE to test the association between pre-post-program changes in TPB beliefs and pre-post-program changes in harvesting and exposure risk reduction behavioral intentions. Similar to the models we used to assess pre-post-program changes, we adjusted for site, age, Alaska Native identity, and gender identity. We also adjusted for changes in other TPB beliefs related to either shellfish harvesting or exposure risk reduction, depending on the behavioral intention outcome.

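### Section 2.5.3 aims to find the most influential TPB constructs but plans no comparison between their coefficients, so its results cannot support a ranking

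*Combined protocol and SAP*

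**What the plan says.** Section 2.5.3 opens with its purpose and method together: "To characterize TPB constructs most influential in shifting planned behaviors, we again used GEE to test the association". The association is between "pre-post-program changes in TPB beliefs and pre-post-program changes in harvesting and exposure risk reduction behavioral intentions". Covariates are carried over from the pre-post models: "we adjusted for site, age, Alaska Native identity, and gender identity". The beliefs are mutually adjusted: "We also adjusted for changes in other TPB beliefs related to either shellfish harvesting or exposure risk reduction", according to which intention is the outcome.

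Section 2.4 describes one instrument with "16 questions relevant to the three types of TPB beliefs", all answered on a 1-5 scale. Section 2.3 gives 50 enrolled. Section 2.5.1 applies listwise deletion to gender, Alaska Native identity and "pre-post-program differences (n missing = 9-15, depending on question".

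The text provided contains no test of a difference between belief coefficients, no relative-importance measure, no ranking rule, no alpha and no multiplicity rule for this analysis. Appendices 2-5 were not available to check.

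**The concern.** Asking which constructs are most influential is a question about differences between coefficients. Testing each coefficient against zero answers another question. One belief may be significant and another not while the two estimates are fully compatible with each other. Mutual adjustment makes each coefficient conditional on the other beliefs; it does not compare them.

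The purpose clause also implies a direction, from belief to intention. Both sides of the model are changes over the same interval, reported on the same survey, so the order in which they occurred is not observed. The one-year survey cannot supply it: Section 2.5.2 reports 4 respondents, presented individually.

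At stake is the mechanism conclusion. Section 2.2 says that control beliefs were a particular target of the program, and this analysis would be read as supporting or contradicting that choice.

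**Working it through.** **Figures in the plan.** There is no power, alpha or effect size for this analysis, so no design figure can be reproduced. Enrolment adds up: 11 + 20 + 19 = 50.

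**Inputs from the documents**
- Complete change scores: 50 − 15 = 35 to 50 − 9 = 41.
- Listwise deletion for gender (10) and Alaska Native identity (6) may reduce this further. With no overlap, and counting persons, 41 − 16 = 25 and 35 − 16 = 19. Neither the overlap nor the counting unit is clear, so I use n of 25-41.
- Covariate terms: site 2 + age 1 + Alaska Native identity 1 + gender 2 = 6.
- Three constructs. The number of belief terms per model is not stated.

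**Assumptions**
- Two-sided 0.05.
- Three belief changes, each with SD 1, equal true coefficients b and mutual correlation 0.3.
- One change score per person, in which case an identity-link GEE reduces to a linear model.

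**Explained variance.** The belief part of intention change has variance b²(3 + 6 × 0.3) = 4.8b².
- b = 0.2, residual variance 1: 0.192/1.192 = 0.16.
- b = 0.3, total variance 1: 0.432.
- b = 0.4, residual variance 1: 0.768/1.768 = 0.43.
- b = 0.4, total variance 1: 0.77, the very favourable case.

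**Central case** (correlation 0.3, R² 0.4, 2,000 simulated studies per row, model-based standard errors)

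| n | Some but not all significant | Exactly one | All three | Joint equality test rejects |
|---|---|---|---|---|
| 25 | 58.8% | 44.8% | 1.8% | 5.7% |
| 30 | 69.1% | 48.8% | 2.6% | 4.6% |
| 35 | 76.4% | 48.4% | 3.9% | 4.8% |
| 41 | 79.8% | 43.4% | 8.5% | 5.6% |

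The beliefs are equal by construction, so every mixed pattern is a difference in significance without a difference in effect.

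**Range**
- R² about 0.16-0.43: mixed in about 29-64% at n = 25 and 38-83% at n = 35-41. Exactly one is significant in about 25-51%, and the joint test rejects in 4-6%.
- R² 0.77, n = 35-41: mixed in 7-17%.
- Correlation 0-0.5, R² 0.2-0.6, n 25-41: mixed in 12-84% and exactly one in 0.4-54%. The low end is n = 41, uncorrelated beliefs and R² 0.6.
- Six belief items instead of three (correlation 0.3, R² 0.2-0.6, n = 30 and 41): mixed in 35-91%.

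**Checks on the remedy**
- With uncorrected sandwich errors at n = 30 and 41, the equality test falsely rejects in 14-21%, so it needs a small-sample correction.
- Joint rejection does not identify a leader. With true coefficients 0.4, 0.4 and 0 it rejects in 20-40% at n = 35-41, although two constructs tie for first.
- With one truly dominant belief (0.4 against 0.1 and 0.1) it rejects in only about 10-19% at n = 25-41.

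**The case against.** **No selection rule is written.** A reader might infer that the plan picks winners by significance. That is the natural reading of a purpose clause joined to a test of association, but it is not stated, and the section title speaks only of relationships. This stands. The gap remains under the alternative, because ranking by size always puts one belief on top and no planned step shows that it differs from the rest.

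**The coefficients can be ordered.** It would be too strong to say that they cannot be ranked, or that each belief is modelled alone. They are mutually adjusted and share a 1-5 response scale, so they can be ordered descriptively with intervals. What is missing is the comparison.

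**The rates rest on assumptions.** They do. Correlation, explained variance, analysed n and number of belief terms are all unstated. The mixed count also includes two-of-three patterns, which name no single winner; this is why the exactly-one rate is given beside it.

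**Same-day answering.** One might go further and say that a shared answering tendency on the day creates the associations. An assumed 30% share of occasion noise gave 23-30% false positives for an unrelated belief, but the documents give no basis for that share, the figure was not independently repeated, and an equality test would not cure it. The supportable point is only that direction is not established.

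**Importance.** This is an explanatory analysis. Section 2.2 makes the pre- and post-program surveys the primary measure, and Section 2.6 adds interviews that give context to the same beliefs. Both points limit the weight of the concern, but neither supplies the missing comparison.

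**Conclusion.** The concern holds in a limited form. As described, Section 2.5.3 can report that changes in a belief were associated with changes in an intention. It cannot show that one construct was more influential than another, nor that belief change came before intention change.

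Under the stated assumptions, equally important beliefs would often give a pattern that invites a ranking. The size of that risk is uncertain, and it is small in the most favourable settings. The absence of a planned contrast does not depend on the simulation. The results and conclusions are not in the documents, so nothing here shows that a wrong construct was in fact named. The primary pre-post comparison is unaffected.

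**What to change.** For each intention outcome:
1. Report all belief-change coefficients from one model on the common 1-5 scale, with confidence intervals. Give standardized coefficients as a sensitivity analysis.
2. Add a joint test that the belief coefficients are equal, and intervals for all pairwise differences. Use a small-sample-corrected variance with a t or F reference, and pool over imputations where imputed data are used.
3. Call a construct most influential only if its pairwise differences from every other construct exclude zero in its favour. Joint rejection alone is not enough.
4. Otherwise report associations without ranking. In either case, state that simultaneous changes do not show which came first.

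This needs no new data: a few post-estimation commands per model, the corrected variance, and revised wording. The real cost is that, with about 10-19% joint rejection even for a clearly dominant belief, a ranking will usually not be supported. In practice the wording change will do most of the work.

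### Section 2.5.3 appears to apply GEE to one pre-post change per student; with at most 35-41 students per question, linear regression with a t reference is a cheap improvement

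*Combined protocol and SAP*

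**What the plan says.** Section 2.5.2 models pre- and post-program responses and explains the method: "we used generalized estimating equation linear regression (GEE) to cluster pre-post measures". Section 2.5.3 turns to the relation between changes in beliefs and changes in behavioral intentions, and there "we again used GEE to test the association between pre-post-program changes in TPB beliefs" and those in intentions. Its models adjust for site, age, Alaska Native identity and gender identity, and for changes in the other beliefs "related to either shellfish harvesting or exposure risk reduction, depending on the behavioral intention outcome".

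Section 2.3 gives the sample: "for a total of 50 participants across communities". Section 2.5.1 treats the changes as variables with their own missing counts, "pre-post-program differences (n missing = 9-15, depending on question"), and removes incomplete cases by "listwise deletion, excluding cases from analysis if data was missing, for gender (n missing = 10"), and likewise for Alaska Native identity (6 missing) and the changes themselves. On imputation it says that "the largest fraction of missing information (FMI) was 0.55, suggesting that our analysis based on 80 imputed datasets was reasonable".

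For 2.5.3 the text names no record unit, cluster unit, variance estimator, reference distribution or small-sample correction.

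**The concern.** GEE is useful when a subject contributes several correlated records. Once the two visits are subtracted, that pair is gone and the reason given in 2.5.2 no longer applies. What GEE then adds to ordinary regression is only its large-sample inference: a normal reference and, depending on the option chosen, a variance that makes no allowance for the parameters fitted. With about 40 students and ten or more parameters, every uncorrected variant gives intervals that are too narrow.

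This matters because 2.5.3 is meant to show which beliefs do most to move intentions. Its output is largely which belief changes show an association, so false positives bear directly on the conclusion.

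**Working it through.** The plan states no error rate for this analysis, so there is no figure of its own to reproduce. A two-sided 5% test is assumed.

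**1. Records per student.** Three features of the text point to one record per student per model: missing changes are counted per question (2.5.1), the adjustment set depends on which intention is the outcome, which implies one outcome per model (2.5.3), and no other cluster unit is named. A numerical check with one record per cluster confirmed that identity-link GEE gives the OLS coefficients (difference about 1e-15), and that its sandwich standard errors equal the uncorrected heteroscedasticity-robust ones (HC0).

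**2. Students available.** 50 - 15 = 35 to 50 - 9 = 41 per change. Fewer may remain once gender, identity and several changes must all be present.

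**3. Parameters.** Intercept 1 + site 2 + age 1 + Alaska Native identity 1 + gender 2 = 7. The number of belief terms is not stated. Three are assumed, one per belief type in the Theory of Planned Behavior, so p = 10 and n - p = 25 to 31.

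**4. False-positive rate under a true null.** The first two rows and the last are exact for normal errors with equal variances. The sandwich row is simulated, with at least 40,000 runs per cell; covariate shares and a belief correlation of 0.3 are assumed.

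| Inference | Formula | n=41 | n=35 |
|---|---|---|---|
| Variance RSS/(n-p), normal reference | 2P(t_{n-p} > 1.96) | 5.9% | 6.1% |
| Variance RSS/n, normal reference | 2P(t_{n-p} > 1.96·√((n-p)/n)) | 9.8% | 11.0% |
| Uncorrected sandwich, normal reference | simulation | 11.7% | 13.3% |
| OLS with t on n-p df | by construction | 5.0% | 5.0% |

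For n=35, RSS/n: √(25/35) = 0.845 and 1.96 × 0.845 = 1.657, so 2P(t_25 > 1.657) = 11.0%.

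Relative to OLS with t (critical values 2.040 on 31 df and 2.060 on 25 df), intervals are 4-5% too narrow in the first row and 16-20% in the second. For n=35, second row: 1.657/2.060 = 0.804. In a separate simulation with rounded Likert-type changes, OLS with t stayed between 4.7% and 5.3%.

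**5. Does pooling supply the correction?** Large-sample Rubin degrees of freedom are at least (80 - 1)/0.55² = 79/0.3025 = 261, so the critical value is at most 1.969. Using 1.969 in place of 1.96 moves the first row only to 5.8-6.0% and the second to 9.7-10.9%.

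**6. Unequal variances.** In an assumed scenario with error SD 0.5+|x|, n=41 and three belief terms, OLS with t runs at 15.1% and the uncorrected sandwich at 16.0%. Over n=35-41 and three to six belief terms, HC3 with t stays at 3.4-4.8% in that scenario. Under equal variances it runs at about 2-3%.

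**The case against.** The strongest reply is that the one-record structure is never stated. Section 2.5.1 describes a file in which each person-visit is an observation, and 2.5.3 says that the earlier method was used again, so stacked rows clustered by student are possible. That stands as a limit. If records were stacked by visit, the point about a missing pair falls. A small-sample concern would remain: in a simulation with two rows per student, uncorrected robust GEE ran at about 9-10% at n=35-41.

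It can also be said that GEE is not itself an error, since the coefficients are those of OLS, and that with RSS/(n-p) the excess is about one percentage point. Both statements are true. They do not dispose of the point, because every uncorrected variant errs in the same direction, the text does not show which one was used, and a better method is available on the same data.

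A reader might infer more: that the false-positive rate is as high as 16%, or 36%. The documents do not support this. The 16% needs six belief terms, a number stated nowhere. The 36% also needs n=19 (50 - 15 - 10 - 6), which requires every missing gender and identity value to be a different student with no overlap with those missing a change. Section 2.5.1 gives neither the unit nor the overlap of those counts.

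**Conclusion.** The point holds as a cheap improvement to a secondary analysis. With one change per student, three belief terms, n=35-41, equal variances and no small-sample correction, the nominal 5% rate becomes about 6%, 10-11% or 12-13% according to the unstated variance estimator. It rises with more belief terms or a smaller n. If a small-sample correction was in fact used, most of the problem disappears.

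It would be wrong to conclude that the findings of 2.5.3 are false, or that the pre-post comparison in 2.5.2 is compromised. The coefficients are unaffected, 2.5.2 does have pairs to cluster, and no 2.5.3 results were available for this review.

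**What to change.** In 2.5.3, fit linear regression on the changes with residual variance RSS/(n-p) and t on n-p degrees of freedom, using Barnard-Rubin small-sample degrees of freedom when pooling imputations. Beside it, report a small-sample robust version, such as HC3 with t, as a sensitivity analysis, because OLS with t is also inflated when variances are strongly unequal. If a covariate level holds a single student, HC3 is undefined; report OLS with t alone and say so.

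For each model, state the record and cluster unit, n, number of parameters and variance estimator. If records were in fact stacked by visit, keep GEE, say so, and apply a small-sample variance correction with a t reference.

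The study has ended ("When we closed the study on July 31, 2024"), so this should be labelled a post hoc change. It needs a different command on existing data and no new collection. The cost is wider intervals and some loss of power, especially with HC3, and some associations may lose significance.

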2.6 Interview Structure

Together with the surveys, pre- and post-program structured interviews followed a convergent parallel study design, with interviews contextualizing the beliefs and behavioral intentions measured in surveys. For example, interview questions related to normative beliefs asked: “How do the people in your life (friends, family, etc.) feel about subsistence clam harvesting? What do you think of their feelings towards subsistence clam harvesting? Have these individuals’ feelings about subsistence clam harvesting influenced how you feel about harvesting? If so, how?” Like the survey, interviews were organized by TPB constructs. The 10 question interview script is included as appendix 5.

2.7 Interview Data Analysis

Interview audio recordings were transcribed using Otter.ai transcription software. Coauthors who conducted interviews reviewed these initial transcripts for quality control, listening to each recording and editing transcripts for accuracy. A codebook was generated

using both inductive and deductive approaches. First, codes were identified based on major themes in the interview protocol and relevant to the TPB. Next, all transcripts were reviewed to identify further themes not captured in deductively developed codes. This grounded theory approach was important to identify new themes raised by participants. The inductive coding process was open and collaborative, with members of the research team involved in the process meeting frequently during coding scheme generation and coding. Each interview was coded by a minimum of two research team members. To support high intercoder reliability, team members checked intercoder agreement and collaboratively reviewed coding results throughout the coding process, identifying differently coded excerpts and reaching consensus on correct coding. Data was coded and analyzed using Dedoose software (Dedoose Version 9.2.12, 2021).
